8.1. Primary Efficacy Analysis

8.1.1. Scalp Investigator Global Assessment (S-IGA)

The S-IGA is an ordinal scale with 5 severity grades which is reported only in integers. Table 3 illustrates the description of each severity grade.

Table 3: S-IGA

Score	Grade	Description
0	Clear	Plaque thickening = no elevation or thickening over normal skin Scaling = no evidence of scaling Erythema = none (no residual red coloration but post-inflammatory hyperpigmentation may be present)
1	Almost Clear	Plaque thickening = none or possible thickening but difficult to ascertain if there is a slight elevation above normal skin level Scaling = none or residual surface drying and scaling Erythema = light pink coloration
2	Mild	Plaque thickening = slight but definite elevation Scaling = fine scales partially or mostly covering the lesions Erythema = light red coloration

Score	Grade	Description
3	Moderate	Plaque thickening = moderate elevation with rounded or sloped edges Scaling = most lesions at least partially covered Erythema = definite red coloration
4	Severe	Plaque thickening = marked or very marked elevation typically with hard or sharp edges Scaling = non-tenacious or thick tenacious scale, covering most or all of lesions Erythema = very bright red coloration; extreme red coloration; deep red coloration

For this study, the primary estimand is the odds of achieving S-IGA success at 8 weeks; that is, the ratio of the odds of achieving S-IGA success at 8 weeks roflumilast foam 0.3% relative to the odds of success at 8 weeks of using a matching vehicle cream. In the course of the 8-week randomized treatment period, subjects may be exposed to possible known or unknown intercurrent events that could possibly impact the estimand, such as treatment discontinuation due to a specific adverse effect or perhaps a lack of effect. The “Treatment Policy Strategy” has been adopted for handling all known or unknown intercurrent events in this study. To this end, the ITT principle will serve as the analytical basis for interpreting the estimand. In other words, the odds ratio of achieving S-IGA success for roflumilast foam 0.3% relative to vehicle at 8 weeks will be evaluated regardless of the occurrence of any such intercurrent event. This estimand shall be estimated using the CMH approach. This approach produces an estimate that is the combined odds ratio resulting from adjusting for the possible effects of 3 classification factors: country, baseline S-IGA category (2 vs. ≥ 3) and baseline B-IGA category (2 vs. ≥ 3).

Categorical Data Analysis

The primary efficacy endpoint is success in S-IGA of disease severity, defined as an S-IGA of “Clear” or “Almost Clear” plus a 2-grade improvement from baseline at Week 8.

The primary endpoint will be analyzed using a CMH test stratified by country, baseline S-IGA category, and baseline B-IGA category. Statistical significance will be concluded at the 5% significance level (2-sided) or less, as discussed in Section 6.1.3. Odds ratios and 95% CIs for the odds ratios will be provided. Additionally, the 95% Wilson CIs for proportion of successes in each treatment group will be presented.

For the primary analysis, missing S-IGA scores will be imputed using multiple imputation as described in Section 6.1.4.1. These imputations will result in a minimum of 25 to a maximum of 250 complete analysis datasets, depending on the number of imputed monotone datasets required. The CMH analyses will be performed separately for each of the complete analysis data sets, and the results will be combined into one multiple imputation inference (estimated treatment effect and associated CI and *P* value). As a sensitivity analysis, the above described CMH test will be performed on the nonimputed data.

Sensitivity analyses of the primary endpoint will also be performed using the original (nonimputed) dataset. These will include a repeated measures logistic regression model (GEE) with S-IGA success as the dependent variable and treatment, country, visit, and baseline S-IGA score as the independent variables.

Achievement of a score of clear will also be analyzed using the CMH test, on nonimputed data.

A tipping point analysis will be performed as described in Section 6.1.4.2. For the tipping point analysis, a figure will be provided that displays the P values in the analysis plotted against the range of shift parameters; included in this figure will be the shift parameters and P values for the range of shift parameters to provide information on where the analysis tips from significant to non-significant.

Subgroup Analyses – Observed Data

For the primary endpoint of IGA success (S-IGA of “Clear” or “Almost Clear” plus a 2-grade improvement from baseline at Week 8), the CMH analysis will be performed on the following subgroups, using observed data:

- Topical Corticosteroids – Naïve Subjects
- Topical Vitamin D Derivatives – Naïve Subjects
- Psoriasis involvement on the knee and/or elbow
- Subjects who achieved both S-IGA and B-IGA success at Week 8
- By Study Site

Subgroup Analyses – Multiple Imputation Data

For the primary endpoint of IGA success (S-IGA of “Clear” or “Almost Clear” plus a 2-grade improvement from baseline at Week 8), the CMH analysis will be performed on the following subgroups, using multiple imputation data:

- Baseline S-IGA = 3
- Baseline S-IGA = 4
- Age Category = 12-17 years
- Age Category = ≥ 18 years
- Subjects who achieved both S-IGA and B-IGA success at Week 8

Continuous Data Analysis

Analysis of change from baseline in S-IGA scores at Weeks 2, 4, 8, and 9 will be performed using descriptive summaries (mean, median, inter-quartile range) by treatment group and study visit. These descriptive statistics will also be presented based on the multiple imputation data.

All Analyses

All other missing data for all other analyses and summaries will remain missing and will not be imputed. All weeks will be included in these analyses, although only Week 8 using the ITT population will be included in the testing strategy.

The primary efficacy analysis will be based on ITT population, and all of the above analyses will be repeated for the mITT population.

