3.2. Sample Size and Power

There are approximately 300 subjects planned for this study. Approximately 200 subjects will receive roflumilast foam 0.3% QD; approximately 100 subjects will receive vehicle foam QD. The sample size was selected to provide an adequate number of subjects to compare the efficacy of roflumilast treatment to vehicle and to provide an adequate number of subjects needed for a safety database.

This sample size provides 96% power at the $\alpha=0.05$ level to detect a 22.4% difference between treatment groups for S-IGA Success at Week 8 using a 2-sided Chi-squared test. The results from a recent phase 2b study (ARQ-151-201) of roflumilast cream compared to vehicle treatment were used to estimate the treatment difference, and it is assumed that the S-IGA response in the present study are similar to IGA responses seen with roflumilast cream. Specifically, in the phase 2b trial, 32.2% of subjects reported IGA success in the roflumilast cream 0.3% group and 9.8% of subjects reported IGA success in the vehicle group.

The number of subjects to be enrolled will also provide sufficient power for most secondary

endpoints.

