Odds Ratio (95% CI) [3]	X.XX (X.XX, X.XX)	
P value [3]	X.XXXXX	

Repeat for all Week 4, Week 8, and Week 9.

Abbreviations: B-IGA = body investigator global assessment; CI = confidence interval; S-IGA = scalp investigator global assessment.
Note: Percentages are n/Number of subjects in the ITT population within planned treatment at each visit*100. Baseline is the last non-missing measurement taken before the first application of study drug.
[1] S-IGA Success ("Yes") is defined as an S-IGA score of "Clear" or "Almost Clear" plus a ≥2-grade improvement from baseline; "No" otherwise.
[2] 95% CIs for "Yes" are obtained using Wilson method.
[3] The odds ratio, 95% CI, and P value are obtained from Cochran Mantel Haenszel test (stratified by country, baseline S-IGA category, and baseline B-IGA category) comparing roflumilast foam 0.3% to vehicle. Reference Listings: 16.2.6.1, 16.2.6.2

Table 14.2.1.5.2

Summary of Scalp Investigator Global Assessment (S-IGA) Grades and Success by Study Visit – Observed Data
Categorical Results

ITT Population - Topical Corticosteroids - Naïve Subjects

(Same shell as Table 14.2.1.5.1; add 16.2.4.2 to reference listings; change “Percentages” footnote to be “Percentages are n/Number of subjects in the ITT population that are topical corticosteroids – naïve subjects within planned treatment at each visit*100.”)

Table 14.2.1.5.3

Summary of Scalp Investigator Global Assessment (S-IGA) Grades and Success by Study Visit – Observed Data
Categorical Results

ITT Population - Topical Vitamin D Derivative - Naïve Subjects

(Same shell as Table 14.2.1.5.1; add 16.2.4.2 to reference listings; change “Percentages” footnote to be “Percentages are n/Number of subjects in the ITT population that are topical vitamin D derivative – naïve subjects within planned treatment at each visit*100.”)

Table 14.2.1.5.4

Summary of Scalp Investigator Global Assessment (S-IGA) Grades and Success by Study Visit – Observed Data
Categorical Results

ITT Population - Subjects with Psoriasis Involvement on the Knee and/or Elbow

(Same shell as Table 14.2.1.5.1; add 16.2.4.2 to reference listings; change “Percentages” footnote to be “Percentages are n/Number of subjects in the ITT population that have psoriasis involvement on the knee and/or elbow within planned treatment at each visit*100.”)

Table 14.2.1.5.5

Summary of Scalp Investigator Global Assessment (S-IGA) Grades and Success by Study Visit – Observed Data
Categorical Results

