(Same shell as Table 14.2.1.5.1; add “B-IGA = body investigator global assessment” to abbreviations in alphabetical order; update “Note:” portion of footnote to add in the following text just after “Note:”: Separate multiple imputation steps were used for monotone and non-monotone missing data. For monotone missing pattern, a predictive mean matching model was used to impute missing value for a subject at particular visit having baseline S-IGA score, treatment group, and country as independent variables and study visit as dependent variable. For non-monotone missing IGA values, Markov-Chain Monte Carlo (MCMC) method was used to impute the data at intermediate visits to make the missing data pattern into monotone before applying the predictive mean matching multiple imputation algorithm.)

Table 14.2.1.7.2

Summary of Scalp Investigator Global Assessment (S-IGA) Grades and Success by Study Visit – Multiple Imputation
Categorical Results
ITT Population – Baseline S-IGA = 3

(Same shell as Table 14.2.1.7.1; change “Percentages” footnote to be “Percentages are n/Number of subjects in the ITT population that have a baseline S-IGA score of 3 within planned treatment at each visit”100.”)

Table 14.2.1.7.3

Summary of Scalp Investigator Global Assessment (S-IGA) Grades and Success by Study Visit – Multiple Imputation
Categorical Results
ITT Population – Baseline S-IGA = 4

(Same shell as Table 14.2.1.7.1; change “Percentages” footnote to be “Percentages are n/Number of subjects in the ITT population that have a baseline S-IGA score of 4 within planned treatment at each visit”100.”)

Table 14.2.1.7.4

Summary of Scalp Investigator Global Assessment (S-IGA) Grades and Success by Study Visit – Multiple Imputation
Categorical Results

ITT Population – Age Category = 12-17 Years

(Same shell as Table 14.2.1.7.1; change “Percentages” footnote to be “Percentages are n/Number of subjects in the ITT population that are between 12 and 17 years of age, inclusive, within planned treatment at each visit*100.”)

Table 14.2.1.7.5

Summary of Scalp Investigator Global Assessment (S-IGA) Grades and Success by Study Visit – Multiple Imputation
Categorical Results

ITT Population – Age Category = ≥ 18 Years

(Same shell as Table 14.2.1.7.1; change “Percentages” footnote to be “Percentages are n/Number of subjects in the ITT population that are aged 18 years or older within planned treatment at each visit*100.”)

Table 14.2.1.7.6

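### The SAP has no rule for carrying imputation uncertainty into the per-arm Wilson intervals of the multiple-imputation tables; read literally, those intervals are somewhat too narrow

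*SAP*

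**What the plan says.** SAP 8.1.1 makes multiple imputation the primary analysis of S-IGA success, with 25 to 250 completed data sets. In the same section it adds: "Additionally, the 95% Wilson CIs for proportion of successes in each treatment group will be presented".

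The table shells in SAP 14.2 carry this through. Footnote [2] of the observed-data table, 14.2.1.5.1, states that the 95% intervals for responders "are obtained using Wilson method". The primary multiple-imputation table, 14.2.1.7.1, is specified as "Same shell as Table 14.2.1.5.1; add", followed by edits to the abbreviations and the general note. Footnote [2] is not among the edits. The subgroup and mITT versions (rest of 14.2.1.7.x, and 14.2.1.8.x) build on that shell and change only the footnote on percentages.

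On pooling, SAP 8.1.1 says that the CMH results from the completed data sets will be "combined into one multiple imputation inference (estimated treatment effect and associated CI and" P value. SAP 6.1.4.1, step 3, lists the odds ratio, its interval and the P value. The step 3 code writes out CMH statistics only, and the text after it deals only with transforming the odds ratio and the P value. No step outputs or combines the per-arm proportions.

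**The concern.** SAP 6.1.4.1 justifies multiple imputation by its ability to reflect the uncertainty of the imputed values. A Wilson interval computed at the full arm size treats every imputed score as if it had been observed. In the main table of the primary endpoint, the odds ratio would then carry imputation uncertainty while the success rates beside it would not.

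The shell also asks for one responder count per arm. With 25 or more completed data sets there is no single count, so the programmer must make a choice that the plan does not state.

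Missing Week 8 scores are foreseen. SAP 6.2 lists S-IGA among the assessments that cannot be done remotely, and SAP 5 creates an mITT population to set aside subjects whose Week 8 S-IGA was lost to COVID-19. Those subjects stay in the ITT analysis and are imputed. What is at stake is how precise the descriptive success rates appear, not the primary test.

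**Working it through.** **Inputs.** SAP 3.2 gives the arm sizes: "Approximately 200 subjects will receive roflumilast foam 0.3% QD; approximately 100 subjects will receive vehicle foam QD". It also gives the planning rates, taken from the earlier cream study: 32.2% on active and 9.8% on vehicle. The number of imputations is M = 25, the minimum in SAP 8.1.1. The Week 8 missing rate is not in the documents; 5%, 10% and 20% are assumptions.

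**The plan's own figure.** The documents state no figure for these intervals. The only figure built on the same inputs is the 96% power in SAP 3.2. With pooled rate (64.4 + 9.8)/300 = 0.2473, null SE √(0.2473 × 0.7527 × 0.015) = 0.0528 and alternative SE √(0.322 × 0.678/200 + 0.098 × 0.902/100) = 0.0444, power is Φ[(0.224 − 1.96 × 0.0528)/0.0444] = 99.7%. The 96% is not reproduced. That is a separate matter and does not enter what follows.

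**Step 1: Wilson interval at the full arm size.** Limits are [p + k/2n ± √k · √(p(1−p)/n + k/4n²)] / (1 + k/n), with k = 1.96² = 3.84.
- Active, p = 0.322, n = 200: 26.1% to 39.0%, width 0.1285.
- Vehicle, p = 0.098, n = 100: 5.4% to 17.2%, width 0.1182.

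**Step 2: Wilson interval with Rubin's total variance.** Let U = p(1−p)/n be the within-imputation variance, B the between-imputation variance and f the fraction of missing information, so B = U·f/(1−f). Put r = (1 + 1/M)·B/U and replace k by t²(1 + r), with t on (M−1)(1 + 1/r)² degrees of freedom.

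Worked case, active arm, f = 0.10: B/U = 0.111; r = 1.04 × 0.111 = 0.1156; degrees of freedom about 2,240; t = 1.961; k = 3.846 × 1.1156 = 4.29. The limits become 25.8% to 39.4%, width 0.1356, and 0.1356/0.1285 = 1.056.

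Two cases bracket f: equal to the missing rate (earlier visits carry no information), or half of it (earlier visits help).

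| Assumed missing | Active, f = missing rate | Vehicle, f = missing rate | Extra width, f = missing rate | Extra width, f halved |
|---|---|---|---|---|
| 5% | 26.0-39.1% | 5.3-17.4% | about 3% | about 1% |
| 10% | 25.8-39.4% | 5.2-17.7% | about 6% | about 3% |
| 20% | 25.4-39.8% | 5.0-18.3% | 12-13% | about 6% |

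A larger M changes little: the factor 1 + 1/M falls from 1.04 at M = 25 to 1.004 at M = 250.

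**Step 3: simulated coverage of the unadjusted interval.** 4,000 trials per scenario, values missing completely at random, proper imputation of the binary outcome, with either an uninformative or a correlated (0.6) earlier visit. Monte Carlo standard error is about √(0.95 × 0.05/4000) = 0.3 points.

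| Assumed missing | Uninformative earlier visit (active / vehicle) | Correlated earlier visit (active / vehicle) |
|---|---|---|
| 5% | 94.8% / 95.7% | 95.3% / 95.3% |
| 10% | 93.5% / 94.3% | 94.6% / 94.8% |
| 20% | 91.5% / 91.9% | 93.0% / 94.0% |

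The pooled interval covered 94.9% to 96.1% throughout. The simulation imputes success directly and does not reproduce the SAP's predictive mean matching on the five-grade score, so it indicates size only.

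**The case against.** The SAP nowhere says that an unadjusted Wilson interval will be computed on imputed data. It says Wilson, and a Wilson interval adapted to multiple imputation would satisfy that word. Inherited shells are also weak evidence: footnote [3] of the same shell describes the odds ratio without mentioning pooling, yet SAP 6.1.4.1 and 8.1.1 plainly require it to be pooled. This stands in part. The unadjusted interval is the literal reading, not an express instruction. But for the odds ratio the text supplies the pooling rule that the footnote omits; for the per-arm rates nothing does.

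A reader might also infer that the Wilson interval would be run on all completed data sets stacked as if they were independent subjects, which would make it far too narrow. The documents do not support this: the step 3 code runs by imputation number, and SAP 8.1.1 has each completed data set analysed separately.

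Finally, the intervals are descriptive, enter no test, and the effect is negligible near 5% missing. The imputation model uses earlier S-IGA scores, which points to the milder figures. All of that stands and limits the weight of the point.

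**Conclusion.** The point holds as a gap with a known direction. The plan calls for per-arm Wilson intervals in the multiple-imputation tables and gives no step that brings between-imputation variance into them. Taken at its word, it produces intervals that are too narrow when Week 8 S-IGA is missing.

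The size depends on a missing rate that the documents do not give. At an assumed 5% it has no practical effect; at 10% it is small; at 20% it is visible, with coverage several points below nominal if earlier visits carry little information. These figures assume the SAP's planning rates, full arm sizes, 25 imputations and, for coverage, values missing completely at random.

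It would be tempting to conclude that the primary result is overstated. It is not: the odds ratio, its interval and the P value are pooled across imputations under SAP 6.1.4.1, and the testing strategy in SAP 6.1.3 makes no use of the per-arm intervals.

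**What to change.** In SAP 8.1.1, state that for multiply imputed data the success rate in each arm is the mean over the completed data sets, and that its 95% interval uses Rubin's total variance, either as a Wilson interval adapted to multiple imputation or pooled on the logit scale and transformed back. Name one of the two.

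Replace footnote [2] in Tables 14.2.1.7.x and 14.2.1.8.x accordingly, and print averaged percentages there instead of single responder counts. Leave the ordinary Wilson interval in the observed-data tables, where it is suitable.

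The program needs one addition: step 3 must output the per-arm proportions by imputation as well as the CMH statistics, and then combine them. The downside is slightly wider descriptive intervals.

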3.5. Method of Assigning Subjects to Treatment Groups

Subjects will be randomized and assigned to active drug or vehicle will be made at a 2:1 ratio according to a computer-generated randomization list. Randomization will be stratified by country, baseline S-IGA (S-IGA=2 vs. S-IGA \geq 3), and baseline B-IGA (B-IGA=2 vs. B-IGA \geq 3).

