(Same shell as Table 14.2.1.7.1; change “Percentages” footnote to be “Percentages are n/Number of subjects in the mITT population that achieved both S-IGA and B-IGA success at Week 8 within planned treatment at each visit*100.”)

Table 14.2.1.9
 Summary of Scalp Investigator Global Assessment (S-IGA) Grades and Success by Study Visit – Observed Data
 Tabulation of Fitted Point Estimates from Generalized Estimating Equations for Binary Response
 ITT Population

Study Visit	Roflumilast Foam 0.3% (N=XX)		Vehicle (N=XX)		Treatment Difference (Roflumilast Foam 0.3% vs Vehicle) [3]	
	n [1]	Responder [2]	n [1]	Responder [2]	Odds Ratio	95% CI for OR
Week 2	XX	XX.X %	XX	XX.X %	X.XX	(XX.XX, XX.XX)
Week 4	XX	XX.X %	XX	XX.X %	X.XX	(XX.XX, XX.XX)
Week 8	XX	XX.X %	XX	XX.X %	X.XX	(XX.XX, XX.XX)
Week 9	XX	XX.X %	XX	XX.X %	X.XX	(XX.XX, XX.XX)

Abbreviations: CI = Confidence interval; OR = odds ratio; S-IGA = scalp investigator global assessment.

Note: Percentages are n/Number of subjects in the ITT population within planned treatment at each visit*100. Baseline is the last non-missing measurement taken before the first application of study drug.

[1] Number of subjects at each visit.

[2] Number of subjects with an S-IGA score of “Clear” or “Almost Clear” plus a ≥2-grade improvement from baseline.

[3] Estimates for odds ratio, 95% CI for odds ratio, and P value are from a generalized estimating equations for binary response model, with S-IGA success as the dependent variable and treatment, country, visit, and baseline S-IGA score as the independent variables. An unstructured correlation matrix was used to model the within subject correlation. In case of convergence issues, other covariance structures will be used including Toeplitz, compound symmetry or Autoregressive (1) (AR[1]) covariance structure will be used, following this sequence until convergence is achieved. The odds ratio is the estimate of the odds of having S-IGA response for subjects treated with roflumilast foam 0.3% relative to that for subjects treated with vehicle.

Reference Listing: 16.2.6.1

Table 14.2.1.10

Summary of Scalp Investigator Global Assessment (S-IGA) Grades and Success by Study Visit – Observed Data
Tabulation of Fitted Point Estimates from Generalized Estimating Equations for Binary Response
mITT Population

(Programming note: Same as table shell 14.2.1.9)

Table 14.2.1.11
Summary of Scalp Investigator Global Assessment (S-IGA) – Score of Clear – Observed Data
ITT Population

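### The GEE sensitivity model for S-IGA success omits baseline B-IGA, a randomisation factor, without a stated reason; adding it is a small, free improvement

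*SAP*

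**What the plan says.** SAP 8.1.1 plans a logistic GEE on observed data as a sensitivity analysis of S-IGA success, with "treatment, country, visit, and baseline S-IGA score as the independent variables". Footnote [3] to the shell of Table 14.2.1.9 (SAP 14.2) repeats the list: "with S-IGA success as the dependent variable and treatment, country, visit, and baseline S-IGA score as the independent variables". It adds that "An unstructured correlation matrix was used to model the within subject correlation", with simpler structures if the model does not converge. Table 14.2.1.10 reuses this shell for the mITT population. Baseline B-IGA appears in none of these places.

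Elsewhere the plan treats B-IGA as a standard adjustment factor. SAP 3.5 states "Randomization will be stratified by country, baseline S-IGA", and the sentence goes on to B-IGA, split at 2 against 3 or more (also Protocol 4.3.1). The primary analysis is a "CMH test stratified by country, baseline S-IGA category, and baseline B-IGA category". The ANCOVAs for PSSI, SI-NRS and PSD (SAP 8.2.2 to 8.2.4) and the Cox model (SAP 8.2.2; Table 14.2.3.5, footnote [4]) carry the same three factors. SAP 10, which lists departures from the protocol, does not explain the difference.

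SAP 8.1.1 also plans a second check on observed data: "As a sensitivity analysis, the above described CMH test will be performed on the nonimputed data".

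**The concern.** A sensitivity model is easiest to read when it differs from the primary analysis only where it is meant to. Here a stratification factor drops out of the adjustment set with no reason given.

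This matters because the odds ratio is not collapsible. If B-IGA is prognostic for S-IGA success, an odds ratio averaged over B-IGA lies closer to 1 than the odds ratio within B-IGA strata, even with perfect randomisation and complete data. Part of any gap between the GEE and the primary CMH estimate could then come from the omitted factor alone. The treatment test also becomes slightly less efficient. What is at stake is the interpretation of one supportive table. No confirmatory decision depends on it, because only the Week 8 ITT result of the primary analysis enters the testing strategy.

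**Working it through.** **Inputs from the plan (SAP 3.2 and 8.1.1).** 200 active and 100 vehicle subjects; success rates 32.2% and 9.8%; two-sided α = 0.05.

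**The plan's own figure.** The SAP gives no figure for the GEE. Its only power figure is 96%, for an unstratified chi-squared test. The pooled rate is (64.4 + 9.8)/300 = 0.2473. The SE under the null is √(0.2473 × 0.7527 × 0.015) = 0.0528. The SE under the alternative is √(0.322 × 0.678/200 + 0.098 × 0.902/100) = 0.0444. Power is Φ((0.224 − 1.96 × 0.0528)/0.0444), about 99.7%, so the 96% does not reproduce. The stated figure understates power, and the discrepancy has no bearing on the point made here.

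**Assumptions not in the documents.** The B-IGA mix is taken as 25% at B-IGA = 2. Within each arm, the odds of success at B-IGA = 2 are k times those at B-IGA ≥3, with k from 1 to 5. The marginal success rates are held at the planning values, and allocation is balanced within strata.

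**Without B-IGA (Week 8).**
- OR = (0.322/0.678)/(0.098/0.902) = 4.37; log OR = 1.475.
- SE = √(1/64.4 + 1/135.6 + 1/9.8 + 1/90.2) = 0.369.
- z = 1.475/0.369 = 4.00; Wald power = Φ(4.00 − 1.96) = 97.9%.

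**With B-IGA, worked for k = 3.**
- Vehicle rates of 18.3% (B-IGA = 2) and 7.0% (≥3) average to 0.25 × 18.3 + 0.75 × 7.0 = 9.8%.
- Active rates of 51.2% and 25.9% average to 0.25 × 51.2 + 0.75 × 25.9 = 32.2%.
- The odds at B-IGA = 2 are 1.0475 (active) and 0.2244 (vehicle), so the conditional OR is 4.67 and its log is 1.541.
- Information per stratum is ab/(a + b), where a and b are n·p(1 − p) in each arm. At B-IGA = 2 it is 12.49 × 3.74/16.23 = 2.88. At ≥3 it is 28.77 × 4.86/33.63 = 4.15.
- SE = 1/√7.03 = 0.377; z = 4.09; power 98.3%.
- Relative efficiency of the test without B-IGA is (4.00/4.09)², or 0.958 with unrounded values.

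The same steps over the range of k:

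| k | OR with B-IGA | SE (log OR) with | Power with | Relative efficiency without |
|---|---|---|---|---|
| 1 | 4.37 | 0.369 | 97.9% | 1.000 |
| 1.5 | 4.41 | 0.370 | 98.0% | 0.995 |
| 2 | 4.48 | 0.372 | 98.1% | 0.984 |
| 3 | 4.67 | 0.377 | 98.3% | 0.958 |
| 5 | 5.10 | 0.389 | 98.7% | 0.910 |

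Without B-IGA, every row has OR 4.37, SE 0.369 and power 97.9%. A 50/50 mix changes little: at k = 3 the OR with B-IGA is 4.66 and the relative efficiency is 0.954.

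**Cross-check on a four-visit GEE.** This used 1,500 simulated trials per setting, robust SEs and an independence working correlation (simpler than the unstructured one planned). At k = 3 the mean log OR was 1.485 (SE 0.299) with B-IGA and 1.428 (SE 0.297) without. Mean z was 4.95 against 4.79, and power was about 100% in both. Type I error was 5.4% with and 5.1% without; across k = 1 to 3 it ranged from 5.1% to 5.9%, with a simulation error of √(0.05 × 0.95/1500) = 0.6 points.

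**Away from the power ceiling.** A separate one-visit simulation assumed a true OR of 2.2, well below the plan's 4.37, with 70% at B-IGA ≥3. Adding B-IGA raised power from 56.6% to 57.9% for a 2-fold B-IGA effect and from 55.0% to 58.3% for a 4-fold effect.

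**The case against.** The strongest reply is that the GEE was never meant to mirror the primary analysis. It uses observed data instead of multiple imputation, pools all visits, and enters S-IGA as a score where the CMH uses a category. It lists no treatment-by-visit term, although the shell reports an odds ratio at each visit; for a Week 8 check that is a larger departure than the missing B-IGA. The check that changes only the missing-data handling is already planned: the three-factor CMH on nonimputed data. B-IGA is also absent from other parts of the plan, namely the imputation model (SAP 6.1.4.1) and the log-rank test as described in SAP 8.2.2.

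Most of this stands, and it rules out two stronger readings that a reader might infer. The first is that omitting B-IGA costs precision in the sense of a wider interval. That holds for linear models but not here: the SE of the log odds ratio is 0.369 without B-IGA and 0.369 to 0.389 with it. The estimate shifts and the test loses a little efficiency. The second is that the omission leaves sensitivity to missing data unreadable. It does not, because the stratified CMH on observed data answers that question with the same adjustment set. Adding B-IGA would not make the GEE like-for-like in any case.

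The reply does not supply a reason for dropping this one factor. The other differences follow from the choice of a repeated-measures model; this one does not.

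**Conclusion.** The point holds as a minor, unexplained inconsistency in a supportive analysis. Under assumed B-IGA odds ratios of 2 to 3, the GEE odds ratio at the planning rates would be 4.37 where the B-IGA-adjusted value is 4.48 to 4.67. Test efficiency falls by about 2 to 4% (9% at an odds ratio of 5), and power by under one point. The loss is zero if B-IGA does not predict S-IGA success.

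These sizes rest on an assumed B-IGA mix and prognostic strength, which the documents do not report, and on the planning rates in SAP 3.2. The documents do not support any claim of a wider interval, an invalid test or a threat to the primary conclusion.

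**What to change.** Add baseline B-IGA category (2 vs ≥3) to the GEE independent variables in SAP 8.1.1 and in footnote [3] of Table 14.2.1.9, and carry it into Table 14.2.1.10, which reuses that shell. If the omission is deliberate, state the reason instead.

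The cost is one term in the text, the footnote and the program. B-IGA is collected at Baseline under the schedule of events, so no new data are needed, and no endpoint, alpha allocation or study procedure changes. The edit should be made before unblinding, so that it cannot look like a choice between two fitted models.
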